3.0 PRELIMINARY DATA

3.1 Meta-analysis of BMD loss after TKA (See Prince, et. al.)³⁹

This meta-analysis of 14 studies that quantified distal femur BMD change after primary TKA. In the distal femoral supracondylar region, mean BMD losses of 0.09 [0.05,0.13], 0.14 [0.08,0.20], 0.16 [0.10,0.23], and 0.16 [0.12,0.20] g/cm² were reported 3, 6, 12, and 24 months respectively following TKA. This corresponds to a 9.3%, 13.2%, 15.8%, and 15.4% BMD loss at these time points. In summary, there is a rapid and significant ~15% decrease in BMD in the first 6 months after TKA that is sustained to 24 months. Better understanding regarding how pre-/perioperative bone health optimization may affect BMD loss and the subsequent periprosthetic fracture risk of is essential.

3.2 Distal femoral BMD and cortical thickness after TKA compared to the contralateral (non-operated) side (See Thomas et. al, and Blaty, et. al.^{22, 23})

We initially performed measurements in 1 cm ROI increments to define BMD change throughout the femur (Thomas, et. al.). Based upon that data, we developed and evaluated a standardized technique to measure BMD and cortical thickness utilizing existing atypical femur fracture DXA software. We then compared distal femoral BMD and cortical thickness on the TKA side to the contralateral non-operative leg (Blaty, et. al.).²³ Thirty adults (15 M/15 F) age 59-80 years with well-functioning unilateral, primary TKA 2-5 years after surgery had femoral DXA scans performed. BMD and cortical thickness were measured at ROIs located at 15%, 25%, and 60% of the femur length measured from the distal notch. Femur BMD and cortical thickness were compared between limbs (TKA vs. non-operated side) by paired t-test.

BMD was 9.7%, 9.6%, and 3.2% lower ($p < 0.0001$) in the operated femur at the 15%, 25%, and 60% ROI respectively. Evaluation of this cohort by BMD status (normal, osteopenia, osteoporosis) finds distal femur BMD at the 25% ROI to be 12% lower in those with osteopenia and 10.3% lower in those with osteoporosis. Cortical width was lower by 22% ($p < 0.05$) at the 25% ROI on the TKA side but not at the 15 or 60% ROI, likely due to current software limitations. Importantly, at these distal femur ROIs, BMD reproducibility was excellent, despite

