4.2 Participant recruitment and study design

Study participants will be recruited from the UW Total Joint Program at the American Center. Patients expressing interest in study participation at the time of TKA scheduling will subsequently be contacted by a University of Wisconsin Osteoporosis Clinical Research Program (OCRP) study coordinator. Those expressing study interest will be scheduled at the OCRP where, following informed consent, medical history, collection of FRAX risk factors and a screening DXA of the lumbar spine, bilateral femurs/hips and VFA will be performed.

The overall study design is noted in Figure 1. Briefly, study eligibility will be determined by DXA. Those with osteoporosis who elect ABL will make up the treatment group ($n = 29$). An equal number ($n = 29$) will be recruited into the untreated group, i.e., those with osteopenia and no prior fragility fracture.

At screening, all participants will have a physical examination and blood collected for a metabolic panel, 25(OH)D and parathyroid hormone (PTH) measurement with additional sample to bank for potential future testing related to bone metabolism. Additionally, calcium and PRO questionnaires will be collected consisting of the KOOS JR, VR-12, and Forgotten Joint Survey. Subjects will be advised on how to achieve a daily calcium intake of 1,000-1,200 mg through food plus supplements, if needed, and up to 4000 IU of vitamin D₃ daily (as noted below; section 5.1). Subsequently, for those meeting all inclusion/exclusion criteria, ABL will be initiated in the treatment group approximately 3 months (depending on the surgery schedule) prior to their TKA and serum calcium will be assessed after one month of dosing. Subsequently, all subjects will have lumbar spine and bilateral femur DXA repeated within two weeks prior to TKA (± 7 days from the month -0.25 study visit) and again 6 and 15 months post TKA. At these same visits, PRO questionnaires will be administered and blood will be collected for serum banking.

Figure 1: Study Design Schematic

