5.9 Subject Discontinuation or Early Termination

Subjects will be informed that they have the right to withdraw from study participation at any time for any reason without prejudice to their medical care. The Investigator must withdraw subjects for the following reasons:

- Hypercalcemia (two consecutive measurements of > 10.5 mg/dL) that persists despite ABL dose reduction.
- Severe hypersensitivity to abaloparatide
- Inability to complete study procedures
- Lost to follow-up

The Investigator may withdraw subjects for any of the following reasons:

- Serious adverse events
- Non-compliance or protocol violations
- Incident vertebral or non-vertebral fragility fracture
- Other situations that may harm subjects or compromise study integrity

All subjects withdrawn prior to completing the study should be encouraged to have study procedures scheduled for the Month 15 visit as deemed appropriate by the PI. Subjects who discontinue or are withdrawn from the study will not be replaced.

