8.0 POWER CALCULATION AND DATA ANALYSIS PLAN

Specific Aim 1: Sample size justification: Based on previously collected data by this study team, we assume that the osteoporotic patients will have an average (SD) BMD prior to surgery of 1.15 g/cm² (0.2). We hypothesize that on average there will be minimal (< 0.02 g/cm²) bone loss at the 15 month follow-up. With a SD of 0.2, if we have follow-up data on at least 21 osteoporotic patients, we will have 86% power with a two-sided one-sample t-test to conclude that ABL effectively reduces bone loss less than 0.16g/cm². To account for up to 26.5% attrition previously reported in the pivotal ABL study,⁴³ we will enroll and treat 29 osteoporotic patients under going TKA.

Specific Aim 2: Sample size justification: If we assume that there will be a medium to large (Cohen's D = 0.65) effect in the paired differences of BMD from baseline to 15 months post TKA in an osteopenic population, then we will need to recruit 21 patients to have 80% power to detect this effect size. To account for up to 26.5% attrition we will enroll and follow 29 osteopenic patients under going TKA.

Baseline demographic and characteristic variables will be summarized with mean (SD), median (IQR), or N (%) based on the statistical distribution of the variable. The primary comparison will be on the change in distal femoral BMD at 25% ROI of the surgical leg from 3 months pre-TKA to 15 months post-TKA. We will test for a significant difference in the osteoporotic population versus a null hypothesis of -0.16g/cm² with a two-sided one-sample t-test. Similarly, we will test for a significant change in BMD in the osteopenic population versus a null hypothesis of 0g/cm² with a one-sample t-test. Exploratory analyses will compare the change in BMD over time between osteoporotic patients treated with ALB and untreated osteopenic patients with repeated measures ANOVA while controlling for age, sex, and BMI as covariates and treating patient as a random effect. Changes over time in secondary variables

will be estimated by paired differences and tested for significant changes from baseline with paired t-tests. All tests will be conducted at a 5% significance level.

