If a subject drops out or is lost to follow-up prior to data collection at time of surgery, they will be completely removed from the study and a new participant will take their place. If a subject drops out or is loss to follow-up after surgery, they will remain in the study and we will implement various data imputation methods like last observation carried forward (LOCF) and linear prediction imputation.

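### LOCF, named in Section 8.0 for patients lost after surgery, scores anyone lost before month 6 as having no bone loss and so biases Aim 1 towards benefit; no primary missing-data method is named.

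*Combined protocol and SAP*

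**What the plan says.** Section 8.0 treats dropouts differently according to timing. Those lost before the surgery-time data collection are removed and replaced. Those lost later are kept in the analysis, and their missing values are filled in as follows: "we will implement various data imputation methods like last observation carried forward (LOCF) and linear prediction imputation". The list is open, no method is called primary, and linear prediction is not defined.

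Section 4.2 and Table 1 schedule DXA at screening, shortly before surgery, "and again 6 and 15 months post TKA". There is no scan between surgery and month 6.

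Section 3.1 gives the expected course without treatment: "mean BMD losses of 0.09 [0.05,0.13], 0.14 [0.08,0.20], 0.16 [0.10,0.23], and 0.16 [0.12,0.20] g/cm² were reported 3, 6, 12, and 24 months respectively". It summarises that "there is a rapid and significant ~15% decrease in BMD in the first 6 months after TKA that is sustained to 24 months".

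Aim 1 tests the treated osteoporotic group "versus a null hypothesis of -0.16g/cm² with a two-sided one-sample t-test". Aim 2 tests the osteopenic group "versus a null hypothesis of 0g/cm² with a one-sample t-test". Section 8.0 measures the primary change from 3 months before TKA, whereas Section 5.4 measures it from immediately before surgery.

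**The concern.** Carrying the last value forward assumes that nothing changes after the last scan. For a patient last scanned before surgery, that contradicts Section 3.1, which places most of the loss in the first six months. If the baseline is the pre-surgery scan, the carried-forward change is exactly zero. If it is the scan about 3 months before TKA, the change is whatever happened before surgery, including any gain on ABL.

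A value of zero counts as complete protection when the null is -0.16. Aim 1 has no concurrent control in which the same error could cancel, so each such patient moves the estimate towards a drug effect. Because several methods are allowed and none is primary, the choice could also be made after the results are known. The main efficacy conclusion is at stake.

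**Working it through.** **The plan's own figures.** Aim 1 assumes a loss of 0.02 on ABL against 0.16, a difference of 0.14, with SD 0.20 and 21 patients with follow-up. The exact two-sided one-sample t-test (20 df, noncentrality 0.14/0.20 × √21 = 3.21) has power 86.2%, matching the stated 86%. Enrolment is 21/(1 - 0.265) = 28.6, so 29. Both reproduce, and neither uses imputed values.

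**Inputs for the check.**
- From the documents: N = 29; 29 - 21 = 8 losses (26.5% of 29 is 7.7); untreated change -0.14 at month 6 and -0.16 from month 12; null -0.16; 5% two-sided test; SD 0.20.
- Assumed: the drug is inactive; all 8 losses occur after surgery and are unrelated to outcome; no mean pre-operative change; correlation 0.8 between month-6 and month-15 changes; scan noise SD 0.015. SD 0.10 is an assumed alternative. Section 8.0 introduces 0.20 beside the mean pre-surgery BMD and then uses it for the test of change, so the SD of change could be smaller.

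**Mean under LOCF.** With E losses before month 6 and 8 - E after it:

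mean = [21 × (-0.16) + (8 - E) × (-0.14) + E × 0] / 29

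For E = 4 this is (-3.36 - 0.56)/29 = -0.135. For E = 8 it is -3.36/29 = -0.116.

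**Chance of falsely declaring benefit** (simulation; nominal 2.5% in this direction):

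| Lost before month 6 (of 8) | LOCF mean | SD 0.20 | SD 0.10 (assumed) |
|---|---|---|---|
| 0 | -0.154 | about 3.5% | about 5% |
| 2 | -0.145 | about 6% | about 10% |
| 3 | -0.140 | about 8% | about 14% |
| 4 | -0.135 | about 10% | about 20% |
| 8 | -0.116 | about 24% | about 54% |

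Analysing only the 21 completers under the same assumptions gives a mean of -0.160 and a rate of 2.5%.

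**Losses after month 6.** LOCF carries -0.14 where -0.16 is expected, an error of 0.02. The first row shows how little this matters.

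**Aim 2.** Zeros pull the mean towards the null of 0. With 4 of 29 lost early, the estimated loss shrinks by about 4/29 = 14%. The test becomes conservative, but the aim is to estimate the loss, and that estimate is too small.

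**Linear prediction, if it means a straight line through a patient's own scans.**
- Lost after month 6, two points (0 at month -0.25, -0.14 at month 6): -0.14 × 15.25/6.25 = -0.34 at month 15.
- Lost after month 6, three points (0 at months -3 and -0.25, -0.14 at month 6): the least-squares slope is -0.0167 per month, giving -0.28.
- Lost before month 6: only pre-operative points exist, so the prediction is about zero if there is no pre-operative trend.

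On this reading it overstates loss by 0.12 to 0.18 for later losses and repeats the LOCF error for early ones.

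**The case against.** The case on the other side is substantial, and most of it limits the size of the point.

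- A reader might infer that both named methods contradict the protocol's time course. The documents do not support that. After month 6, LOCF nearly agrees with the plateau. Linear prediction is undefined and could mean regression of the month-15 value on month 6 and covariates, which need not conflict with Section 3.1. The firm defect there is that it is not specified.
- A reader might take 24% to 54% as the expected error. Those figures need all 8 losses to fall between surgery and month 6, and the upper one also needs an assumed SD. The 26.5% is total attrition from another study, with no timing given. If 8 losses were spread evenly over 15 months, about 8 × 6/15 = 3 would fall before month 6, giving about 8% at SD 0.20.
- Under Section 8.0, losses before surgery are replaced, not imputed. Section 5.9 says withdrawn subjects are not replaced, and the two statements need reconciling.
- Section 5.9 encourages withdrawn subjects to attend the month 15 procedures, and anyone scanned then needs no imputation. This reduces the problem without removing it, since attendance is not assured.
- Section 5.9 lists "Incident vertebral or non-vertebral fragility fracture" as a reason for withdrawal, which suggests dropout related to bone loss. It is only a permitted reason, and nothing shows how often it would apply.
- The plan does not commit to LOCF as the primary method, and imputation might be meant as supportive. That is fair, but nothing in Section 8.0 says so.

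What remains is that LOCF is unsuitable for losses before month 6, and the plan leaves it available for the primary test.

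**Conclusion.** The point holds for patients lost between surgery and month 6. LOCF scores them at about zero change, or at a gain if the baseline is month -3 and BMD rose before surgery. The bias favours the drug in Aim 1. At the plan's SD of 0.20, with 8 of 29 lost, false benefit rises from 2.5% to about 6% to 10% with 2 to 4 early losses, and to 24% at worst. It is higher if the SD of change is smaller. These rates assume an inactive drug and dropout unrelated to outcome, and they depend on a timing of loss that the documents do not give. LOCF can therefore create a false finding, but it cannot be said that it will. A false finding of loss in Aim 2 does not follow, because there LOCF only understates the loss. For linear prediction, the conclusion is that the term must be defined or dropped.

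**What to change.** First reconcile the baseline between Sections 5.4 and 8.0. Then amend the dropout paragraph of Section 8.0:

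- Remove LOCF and any extrapolation over time from the primary analysis.
- Name one primary method: either a likelihood-based repeated-measures model with visit as a category (month -3, pre-surgery, month 6, month 15) fitted to all observed data, or multiple imputation from the observed visits. Test the month-15 mean change from the agreed baseline against the null.
- Patients lost before month 6 have no post-operative data, so either method rests on an untestable assumption for them. Add a sensitivity analysis that assigns treated dropouts the -0.16 benchmark loss, and a tipping-point analysis.
- Report the number lost before and after month 6.

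The cost is a rewritten paragraph, slightly more analysis work and slightly wider intervals. The stated 86% power rests on 21 observed patients and is unaffected.

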8.1 Study timeline

This study is planned to span 3 years (Table 1). The first month will be spent finalizing the protocol, designing recruitment material and establishing resources in the UW system. Months 2-3 will be dedicated to obtaining IRB approval and ensuring the project is compliant with other regulatory requirements. Study tools, materials and recruitment pathways will also be finalized during this time, with the anticipation that subject recruitment will begin in month 4. Our goal is to enroll 5-6 subjects per month and complete study enrollment in 12 months. This has our final visits occurring in year 3, around 33 months. In year 3, study staff will dedicate time to conducting final visits, cleaning data and performing final analyses. It is planned that preliminary data will be used to submit abstracts to key meetings in the bone fields (Orthopedics and Medicine) including AAHKS, AOA, ASBMR, ISCD and perhaps IOF. Final manuscripts will be submitted for publication in year 3.

Table 2: Study Timeline

	Year 1												Year 2												Year 3											
Month	1	2	3	4	5	6	7	8	9	10	11	12	13	14	15	16	17	18	19	20	21	22	23	24	25	26	27	28	29	30	31	32	33	34	35	36
Finalize Protocol																																				
Regulatory																																				
Study Prep																																				
Recruitment																																				
Conduct																																				
Data Clean																																				
Analysis																																				
Publication																																				

